10.3.3.2 Serious adverse events that require the investigator to immediately notify the sponsor

The investigator must report all adverse events that meet one of the seriousness criteria below, except for events listed in section 10.3.3.1 as not requiring notification:

- 1- Death
- 2- Life threatening situation
- 3- Requiring hospitalisation or prolonging hospitalisation
- 4- Persistent or significant disability or incapacity
- 5- Congenital abnormality or birth defect
- 6- Or any other adverse event considered "medically significant"

- ❖ For serious adverse events related to the experimental medication(s) and which are expected:
 - the -SmPC for the « **cilostazol** » speciality, found in (Appendix 5), should be consulted.
- ❖ The serious adverse events associated with specific research procedures or exams, and which are expected, are:
 - Poorly tolerated auricular or ventricular arrhythmia
 - Abnormal bleeding (requiring blood transfusion or not)
 - Allergy

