5.7 Distinction between care and research

TABLE: Distinction between procedures associated with "care" and procedures added because of the "research "

Procedures and treatments carried out as part of the research	Procedures and treatments associated with care	Procedures and treatments added because of the research
Treatments	DCI and vasospasm preventive and curative treatments (must include nimodipine administration)	Cilostazol or placebo administration during 14 days
Consultations	Routine visits from the physician in charge	Face to face interview at 6 months

Blood samples	Left to the discretion of the physician	None
Imaging, etc.	Imaging (CT scan, MRI, TCD) left to the discretion of the physician	All the imaging techniques evaluating secondary objectives are routinely realized

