5.8.4 Terminating part or all of the research

Le GHU Paris Psychiatrie et Neurosciences as sponsor or the Competent Authority (ANSM) can prematurely terminate all or part of the research, temporarily or permanently, upon the recommendation of a data and safety monitoring board in the following situations:

- first of all, if suspected unexpected serious adverse reactions (SUSARs) are seen in an arm being treated or if there is a discrepancy in the serious adverse reactions between the 2 arms being treated, and which require a reassessment of the benefit-risk ratio for the research [to be adapted].
- in the case of interim analysis: stopping treatment to demonstrate the efficacy of one of the arms being treated or on the other hand stopping due to futility
- likewise, unexpected facts, new information about the product, in light of which the objectives of the research or of the clinical programme are unlikely to be achieved, can lead Le GHU Paris Psychiatrie et Neurosciences as sponsor or the Competent Authority (ANSM) to prematurely halt the research
- Le GHU Paris Psychiatrie et Neurosciences as sponsor reserves the right to permanently suspend inclusions at any time if it appears that the inclusion objectives are not met.

If the research is terminated prematurely, the decision and justification will be given by the sponsor, Le GHU Paris Psychiatrie et Neurosciences, to the Competent Authority (ANSM) and to the CPP within 15 days, along with recommendations from the Data and Safety Monitoring Board (if applicable).

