10.3.1 Definitions (Regulation (EU) N° 536/2014 (REC)

Adverse event Any untoward medical occurrence in a patient or clinical trial subject administered a medicinal product and which does not necessarily have a causal relationship with this treatment.

- **Adverse drug reaction**

Any response to a medicinal product which is noxious and unintended.

- **Serious adverse event**

Any untoward medical occurrence that at any dose results in death, is life-threatening, requires inpatient hospitalisation or prolongation of existing hospitalisation, results in persistent or significant disability/incapacity, or is a congenital anomaly/birth defect.

- **Unexpected adverse reaction**

An adverse reaction, the nature, severity or outcome of which is not consistent with the applicable product information: the summary of product characteristics (SmPC) for an authorised product or the investigator's brochure for an unauthorised investigational product.

According to the notice to sponsors of clinical trials for medications (ANSM):

- **New safety issue**

Any new information regarding safety:

- that could significantly alter the assessment of the benefit-risk ratio for the experimental medication, or for the trial
- or which could lead to the possibility of altering the administration of the experimental medication or altering the conduct of the trial

Examples:

- a) any clinically significant increase in the frequency of an expected serious adverse reaction occurring
- b) suspected unexpected serious adverse reactions (SUSAR) occurring in patients who have finished the trial and about whom the sponsor is notified by the investigator, who also provides any follow-up reports
- c) any new fact relating to the conduct of the clinical trial or the development of the experimental medication, if the new fact is likely to affect participant safety

Examples:

- a serious adverse event likely to be related to the investigations and to the trial's diagnostic procedures and which could modify the conduct of this trial
- a significant risk for the trial participants such as ineffectiveness of the experimental medication used in the trial in treating a life-threatening illness
- significant safety results from a recently completed research carried out on animals (such as a carcinogenicity research)
- the premature termination, or temporary interruption, of a trial conducted with the same experimental medication in another country, for safety reasons

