10.3.6.1 Analysis and declaration of serious adverse events

The sponsor assesses:

- the seriousness of all adverse events reported
- the causal relationship of these events with each experimental medication and/or specific medical procedures/exams added by the research and with other possible treatments
- the expected or unexpected nature of these adverse reactions

All serious adverse events which the investigator and/or the sponsor believe could reasonably have a causal relationship with the experimental medication are considered as suspected adverse reactions.

All suspected unexpected serious adverse reactions (SUSAR) are declared by the sponsor, within the legal time frame, to the Agence Française de Sécurité Sanitaire des Produits de Santé (ANSM, French Health Products Safety Agency) and to the relevant Comité de Protection des Personnes (CPP, ethical committee).

- The initial declaration must be made with no delay after the date on which the serious adverse event occurs in the case of death or of a life-threatening diagnosis.
- The initial declaration must be made with no delay after the date on which the serious adverse event occurs in the case of other serious situations.
- The follow-up declaration must be made with no delay.

Any suspected unexpected serious adverse reaction must also be declared electronically in the Eudravigilance European database for adverse events due to medications, established by the European Medicines Agency (EMA).

The sponsor must notify all relevant investigators about any data that could adversely affect the safety of the research subjects.

Specific cases of serious adverse events of special interest:

At the request of ANSM, the sponsor may be asked to declare serious adverse events of special interest, in accordance with the same procedures and deadlines as SUSARs.

Specific case of double-blind trials

As a general rule, the sponsor declares a suspected unexpected serious adverse reaction to the competent authorities and to the CPP after having broken the blind on the experimental medication.

In exceptional situations, and if the ANSM grants permission when requested by the sponsor in the sponsor's clinical trial authorisation application, the methods for unblinding and for declaring suspected unexpected serious adverse reactions can be modified. These methods will then be defined in detail in the research protocol (see section 4.2.6).

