Appendix 5 Instrumental activities of a daily living

I.A.D.L (INSTRUMENTAL ACTIVITIES OF DAILY LIVING)

OBJECTIF

Les 4 items de l'échelle I.A.D.L de Lawton permettent de dépister les sujets qui présentent une démence non encore diagnostiquée, ou qui la développeront dans l'année.

DESCRIPTIF

Ces 4 items explorent l'autonomie ou le degré de dépendance du sujet par rapport à 4 activités pratiques de la vie quotidienne.

Ces 4 activités doivent faire l'objet d'une cotation de 1 à 2, 3, 4 ou 5 points selon les items. Vous devrez pour chaque item attribuer le score en fonction de la grille de cotation (ci dessous). La cotation est basée sur les réponses du patient et/ou en tenant compte de l'avis de la personne vivant avec lui au quotidien. Dans un deuxième temps, pour fonder votre décision pratique, vous simplifierez la cotation de chacun des items en codage binaire 0 ou 1. Codez 0 : tout item pour lequel le sujet est autonome (la cotation ne dépasse pas 1). Codez 1 : tout item pour lequel le sujet est dépendant (la cotation est supérieure ou égale à 2)

CAPACITE A UTILISER LE TELEPHONE... 0=autonome, 1=dépendant

1. Je me sers du téléphone de ma propre initiative, cherche et compose les numéros, etc.
2. Je compose un petit nombre de numéros bien connus.
3. Je réponds au téléphone, mais n'appelle pas.
4. Je suis incapable d'utiliser le téléphone.

MOYEN DE TRANSPORT 0=autonome, 1=dépendant

1. Je peux voyager seul(e) et de façon indépendante (par les transports en communs ou avec ma propre voiture)
2. Je peux me déplacer seul(e) en taxi, mais pas en autobus.
3. Je peux prendre les transports en commun si je suis accompagné(e)
4. Je ne me déplace pas du tout.

PRISE DE MEDICAMENTS 0=autonome, 1=dépendant

1. Je m'occupe moi-même de la prise (dose et horaires)
2. Je peux les prendre moi-même, s'ils sont préparés et doses a l'avance.
3. Je suis incapable de les prendre moi-même.

GERER SON ARGENT 0=autonome, 1=dépendant

1. Je suis totalement autonome (budget, chèques, factures)
2. Je me débrouille pour les dépenses au jour le jour, mais j'ai besoin d'aide pour gérer mon budget a long terme.
3. Je suis incapable de gérer l'argent nécessaire a payer mes dépenses au jour le jour.

RESULTATS

- 3 ou 4 items sont codes 1 : diagnostic de maladie probable
- 1 ou 2 items sont codes 1 :
 - si la modification est intervenue dans l'année, envisager un Alzheimer
 - si la modification n'est pas intervenue dans l'année :

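### Section 10.3.3.2 lists cilostazol's own major harms as expected events of research procedures, without a severity limit on bleeding or allergy, so serious drug reactions could be misclassified as expected

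*Protocol*

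**What the plan says.** Protocol section 10.3.3.2 covers serious adverse events that must be notified to the sponsor at once. It gives two separate rules on expectedness.

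- **Drug-related events.** The reader is sent to the cilostazol SmPC, "found in (Appendix 5), should be consulted".
- **Procedure-related events.** "The serious adverse events associated with specific research procedures or exams, and which are expected, are": poorly tolerated atrial or ventricular arrhythmia; "Abnormal bleeding (requiring blood transfusion or not"; and allergy.

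Section 10.3.1 defines an unexpected adverse reaction as "An adverse reaction, the nature, severity or outcome of which is not consistent with the applicable product information", meaning the SmPC for an authorised product. Under section 10.3.6.1 the sponsor assesses expectedness, and "All suspected unexpected serious adverse reactions (SUSAR) are declared by the sponsor, within the legal time frame". As a general rule the blind is broken before that declaration. Section 5.8.4 opens its reasons for early termination with "first of all, if suspected unexpected serious adverse reactions (SUSARs) are seen in an arm being treated" and adds, in the same item, a discrepancy between the arms in serious adverse reactions.

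**The concern.** Expectedness decides whether a serious suspected reaction is handled as a single case that must be declared and normally unblinded, or only as part of accumulating data. A list of expected events should therefore name the right cause and say how severe an event may be and still count as expected. This list names the wrong cause, and for bleeding and allergy it sets no limit.

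The trial gives an antiplatelet agent to patients who have just had an intracranial haemorrhage, so bleeding is a central safety signal. If someone classifying a case used the printed list, a fatal or life-threatening drug-related bleed or allergic reaction could be labelled expected. It would then miss case-level declaration and unblinding under section 10.3.6.1, and would not count under the SUSAR limb of section 5.8.4.

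**Working it through.** No arithmetic applies. The check sets the relevant sections side by side.

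1. **Which cause do other sections give for these events?** Section 2.7 names arrhythmia, abnormal bleeding and allergy as the major effects of cilostazol. Section 4.1.2, item 12, makes them the cilostazol-related major adverse events, and section 5.2 collects them daily under that label. All three of the three named major harms appear in the procedure list.

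2. **Does the next section fit this reading?** Section 10.3.3.3 lists well tolerated arrhythmia and then tachycardia, fever, fainting, nausea, vomiting and stomach pain. Those last six are the minor cilostazol-related events of section 4.1.2, item 13. Sections 10.3.3.2 and 10.3.3.3 thus look like one drug-event list split by seriousness, with the serious half under a procedures label.

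3. **Could an added procedure cause them?** Section 5.7 gives, as added by the research, 14 days of cilostazol or placebo and a face-to-face interview at 6 months. Added blood samples are none. In the column for added procedures the imaging entry reads "All the imaging techniques evaluating secondary objectives are routinely realized". In the section 5.5 schedule the row for medical procedures such as ECG is empty. Apart from the study drug, nothing there could plausibly cause arrhythmia, bleeding or allergy.

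4. **Is there a severity or outcome limit?** Section 10.3.1 tests nature, severity and outcome. The bleeding item includes events with and without transfusion and sets no upper bound; the allergy item is one word. Only arrhythmia carries a qualifier, that it is poorly tolerated. Read literally, a fatal bleed or anaphylactic shock falls inside the list.

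5. **Is the governing document where the protocol says?** The page cited for the SmPC is headed "Appendix 5 Instrumental activities of a daily living". The nine appendices in the protocol are the mRS interview, SAHOT, MOCA, ADL, IADL, Charlson score, therapy intensity level, network meta-analysis and Fisher scale. None is an SmPC. Section 7.1.1 says cilostazol is no longer marketed in France and will be imported, and no section identifies or dates the SmPC that applies.

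**Result.** The only list of expected serious events printed in the protocol is the misattributed one, and the text that should correct a reader is not at the place cited.

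**The case against.** The strongest reply is that the protocol's formal rules for drug reactions are sound. The drug bullet in section 10.3.3.2 points to the SmPC, section 10.1 names the same source, and section 10.3.1 includes severity and outcome. Section 10.3.2.2 gives the investigator severity and causality; section 10.3.6.1 gives expectedness to the sponsor. A wrong appendix number does not remove the SmPC from a sponsor that imports the product. By its own terms the three-item list does not govern drug reactions.

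This stands, and it rules out two stronger readings.

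- A reader might infer that the protocol excludes drug-caused fatal bleeds or anaphylaxis from SUSAR declaration. It does not. Under the SmPC bullet and section 10.3.1, such a case is unexpected whenever its severity or outcome is not consistent with the SmPC. The SmPC is not in the document, so how it would classify a given case cannot be checked.
- A reader might infer that these events are kept out of the first termination criterion in section 5.8.4. They are not. Its second limb, the discrepancy between arms, does not require unexpectedness.

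Other safeguards also remain: same-day notification (10.3.2.1, subject to the exceptions in 10.3.3.1); treatment of a clinically significant rise in an expected serious reaction as a new safety issue (10.3.1), declarable within 15 calendar days (10.3.6.2); annual line listing (10.3.6.3); and the DSMB's power to recommend stopping for serious adverse reactions (10.3.7).

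It can also be said that imaging is not clearly care only: the synopsis, under procedures added by the research, mentions imaging at day 10-21, and section 5.2 schedules scans at 24/48 hours and at day 28-45. That leaves the status of imaging less settled than section 5.7 suggests, but it does not explain why the list reproduces cilostazol's three major harms.

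What the reply does not remove is the conflict in the text. Apart from notification, annual listing and DSMB review, the remaining routes depend on a pattern across patients. SUSAR status is what triggers declaration and unblinding for a single case.

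**Conclusion.** The point holds as a risk of misclassification created by an operative safety rule. The list is attributed to procedures that could not plausibly cause the events, has no severity or outcome limit for bleeding or allergy, and conflicts with section 10.3.1; the SmPC reference beside it is wrong. It covers all three named major harms of the drug.

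A loss of SUSARs is possible, not established. It depends on someone applying the printed list to a drug reaction in place of the SmPC. The documents give no rate for these reactions (section 2.7 says the frequency is not reported), so no number of affected cases can be stated. Notification, the between-arm limb of section 5.8.4, the new-safety-issue rule and DSMB review would still operate.

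**What to change.** In the next amendment:

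- Remove the three items from the research-procedures bullet in section 10.3.3.2 and state that no serious adverse event is expected from research procedures.
- Keep arrhythmia, bleeding and allergy as events to be notified immediately.
- State that expectedness of drug reactions is judged only against an identified, dated cilostazol SmPC, by nature, severity and outcome as in section 10.3.1.
- Correct the Appendix 5 reference so that it leads to that SmPC.

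The cost is wording. The possible downside is a few more SUSAR declarations, with unblinding of those patients. No endpoint, sample size or treatment rule changes.

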10.3.3.3 Other events that require the investigator to immediately notify the sponsor

- **Adverse events that are "not serious" but which are significant for the safety of participants**
- The following adverse event will be assessed:
 - Well tolerated arrhythmia from auricular origin
 - Well tolerated arrhythmia from ventricular origin
 - Tachycardia,
 - Fever
 - Fainting

- Nausea
- Vomiting
- Stomach pain
- The investigator must notify the sponsor about these "nonserious" adverse events, in accordance with the same procedures and deadlines as serious adverse events (see section 10.3.4). These events can be considered "medically significant".
- **In utero exposure**

The sponsor must be notified immediately about any pregnancy during which the foetus (from the pre-embryonic stage up to birth) could have been exposed at a given time to an experimental medication, even if the pregnancy is not associated with an adverse event.

Notification is required if the exposure involves:

- the mother,
- the father if the experimental medication is genotoxic.

10.3.4 Procedures and deadlines for notifying the sponsor

Notification of an SAE must initially be provided in a written report using the special form for reporting SAE. The report must be signed by the investigator.

Each item in the form must be completed by the investigator so that the sponsor can carry out the appropriate analysis.

This initial notification must be followed by one or more detailed follow-up report(s), in writing and signed, within a maximum of 8 days in the case of a fatal or life-threatening event and within 15 days for all other cases.

Whenever possible, the investigator will provide the sponsor with any documents that may be useful (medical reports, laboratory test results, results of additional exams, etc.). These documents must be made anonymous. In addition, the documents must include the following: research acronym, number and initials of the subject, nature and date of the serious adverse event.

Any adverse event will be monitored until fully resolved (stabilisation at a level considered acceptable by the investigator, or return to the previous state) even if the subject has left the trial.

The initial notification, the SAE follow-up reports and all other documents must be sent to the sponsor via fax only to the Vigilance Division of the DRCI, [contact]**.

For studies using e-CRF:

- the investigator completes the SAE notification form in the e-CRF, validates, prints and signs the form before sending it *via fax*.
- if it is not possible to connect to the e-CRF, the investigator will complete, sign and send the SAE notification form found in the Investigator Worksheet. As soon as the connection is restored, the SAE notification form in the e-CRF must be duly completed.

The investigator must comply with all requests from the sponsor for additional information.

For all questions relating to the notification of an adverse event, the DRCI can be contacted via email: [contact]

The investigator must monitor the pregnant woman throughout her pregnancy or until the pregnancy is terminated, and must notify the sponsor of the outcome of the pregnancy, using this form.

If the outcome of the pregnancy falls within the definition of a serious adverse event (miscarriage, pregnancy termination, foetal death, congenital abnormality, etc.), the investigator must follow the procedure for reporting SAE.

If the exposure involves the father, the investigator must obtain the mother's permission before collecting information about the pregnancy.

The initial pregnancy notification, the SAE follow-up reports and all other documents must be sent to the sponsor via fax only to the DRCI, [contact]**.

10.3.5 Period for notifying the sponsor

The investigator must report all SAE that occur in research subjects:

- after the date on which treatment with an experimental medication began
- throughout the period during which the participant is monitored, as determined by the research
- for up to 4 or more weeks after the participant stops treatment using the experimental medication
- with no time limit, if the SAE is likely to be due to the experimental medication or to the research procedures (for example, serious reactions that could appear long after exposure to the medication, such as cancers or congenital abnormalities).

10.3.6 The sponsor's roles

The sponsor, represented by its DRCI, continuously assesses the safety of each experimental medication throughout the research.

10.3.6.1 Analysis and declaration of serious adverse events

The sponsor assesses:

- the seriousness of all adverse events reported
- the causal relationship of these events with each experimental medication and/or specific medical procedures/exams added by the research and with other possible treatments
- the expected or unexpected nature of these adverse reactions

All serious adverse events which the investigator and/or the sponsor believe could reasonably have a causal relationship with the experimental medication are considered as suspected adverse reactions.

All suspected unexpected serious adverse reactions (SUSAR) are declared by the sponsor, within the legal time frame, to the Agence Française de Sécurité Sanitaire des Produits de Santé (ANSM, French Health Products Safety Agency) and to the relevant Comité de Protection des Personnes (CPP, ethical committee).

- The initial declaration must be made with no delay after the date on which the serious adverse event occurs in the case of death or of a life-threatening diagnosis.
- The initial declaration must be made with no delay after the date on which the serious adverse event occurs in the case of other serious situations.
- The follow-up declaration must be made with no delay.

Any suspected unexpected serious adverse reaction must also be declared electronically in the Eudravigilance European database for adverse events due to medications, established by the European Medicines Agency (EMA).

The sponsor must notify all relevant investigators about any data that could adversely affect the safety of the research subjects.

Specific cases of serious adverse events of special interest:

At the request of ANSM, the sponsor may be asked to declare serious adverse events of special interest, in accordance with the same procedures and deadlines as SUSARs.

Specific case of double-blind trials

As a general rule, the sponsor declares a suspected unexpected serious adverse reaction to the competent authorities and to the CPP after having broken the blind on the experimental medication.

In exceptional situations, and if the ANSM grants permission when requested by the sponsor in the sponsor's clinical trial authorisation application, the methods for unblinding and for declaring suspected unexpected serious adverse reactions can be modified. These methods will then be defined in detail in the research protocol (see section 4.2.6).

